Primary Hypothesis 1: Clients in the PATH condition will demonstrate higher rates of confirmed substance abstinence (hair and UA verified) during treatment and at follow-up than clients in the SC condition. Confirmed abstinence is the “gold standard” of direct clinical outcomes in SUD research. A mixed effects logistic regression model [2,3] will be used to compare the binary outcome of hair and urinalysis-confirmed abstinence in the two treatment conditions at months 3, 6, 9, 12, 15, and 18. Mixed effects models have advantages of traditional repeated measures approaches in that they allow for missing observations, accommodate measurements made at different time points, provide flexibility in modeling the variance-covariance matrix, and permit the estimation of both group and random patient-specific effects. The model will include terms for treatment condition, time, and their interaction, and the binary baseline abstinence variable along with any other necessary covariates. We will follow the recommendations of Varadhan and Seeger [4] to test heterogeneity of treatment effect (HTE). We have identified two primary subgroup analyses to be performed: (1) setting [IP (n = 400) vs. OP (n = 400)] and (2) type of opioid [heroin (n = 534) vs. prescription (n = 266)]. We will use similar mixed effects logistic regression models (described above) that will additionally include terms for the specific subgroup variable and its interaction with treatment condition. In the event that the interaction is significant, the treatment effect will be estimated separately at each level of the categorical variable that is used to define the subgroups. In addition, we will conduct an *exploratory* subgroup analysis for medication type (agonist vs. antagonist/drug free). We anticipate simple time trends (e.g., linear or quadratic) for the mixed effects models; however, we will use linear spline models in the event complex time trends are observed, such as non-linear trends that cannot be approximated by simple polynomials in time [2]. These analyses will be performed using PROC GLIMMIX.

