Power for the Primary Hypotheses. Power analyses were calculated for the primary hypotheses described above. The power analyses for Primary Hypothesis 1 were calculated following the recommendations of Liu and Wu [8]. The analysis was based on a corrected alpha of .025 (.05/2 primary outcomes), a compound symmetry covariance structure, an estimated abstinence rate of 25% in the SC condition (based on data from our prior study), a correlation between observations on the same patient of .50, and assuming 20% attrition at the final time point. For the smallest subgroup (patients primarily using prescription opioids: $n = 266$; 133 per condition), we will have 80% power to detect an approximately 15% difference in abstinence rates between the conditions (i.e., 25% in control vs. 40% in experimental; OR = 2.0). This projected difference is conservative and based only on the repeatedly demonstrated, similarly scaled differences contingency management yields when compared to standard treatment conditions [9-13]. The smallest detectable differences for the remaining subgroups and the overall sample are as follows using the same specifications: (1) patients recruited from IP setting ($n = 400$): 12%, OR = 1.8, (2) patients recruited from OP setting ($n = 400$): 12%, OR = 1.8, (3) patients primarily using heroin ($n = 534$): 9%, OR = 1.6, and (4) the overall sample ($n = 800$): 8%, OR = 1.5. The power analyses for Primary Hypothesis 2 were calculated following the recommendations of Lakatos [14]. The analysis was based on a corrected alpha of .025, no attrition as chart data will be available for all patients, and estimated dropout rate of 60% in the SC condition [15]. For the smallest subgroup (patients primarily using prescription opioids: $n = 266$; 133 per condition), we will have 80% power to detect a hazard ratio of .59 which corresponds to a difference in survival rates of approximately 18% between the two conditions. The smallest detectable hazard ratio for the remaining subgroups and overall sample are as follows using the same specifications: (1) patients recruited from IP setting ($n = 400$): HR = .65, 15% difference in survival (2) patients recruited from OP setting ($n = 400$): HR = .65, 15% difference in survival (3) patients primarily using heroin ($n = 534$): HR = .69, 13% difference in survival, and (4) the overall sample ($n = 800$): HR = .74, 10% difference in survival. We have chosen to use an alpha level that corrects for the number of primary hypotheses rather than the number of subgroup analyses as the latter approach would substantially increase the likelihood of making a type 2 error [4,16].

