Heterogeneity of treatment effects. The subgroup analyses described above will be used as a test of the heterogeneity of treatment effects. In addition, we have identified three patient characteristics that may be related to treatment effects: psychiatric problem severity (meets pre-determined threshold vs. does not), OUD problem severity (meets pre-determined threshold vs. does not), and housing status (homeless or housed). Each of these variables should negatively impact treatment outcomes, and could suppress differences between conditions. To evaluate the heterogeneity of treatment effects as a function of psychiatric severity, the mixed effects models and survival analyses used to test the primary hypotheses will be modified to include a binary term reflecting psychiatric severity and the interaction of psychiatric severity and condition. A significant interaction would indicate that the effects of the intervention vary as a function of a patient's psychiatric severity (i.e., treatment effects are heterogeneous). If the interaction term is significant, the treatment effect will be estimated separately at each level of the categorical variable that is used to define the subgroups. Similar analyses will be performed for OUD problem severity and housing.

References

7. Allison PD. *Survival analysis using SAS: A practical guide*. SAS Institute; 2010.

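### For abstinence, the severity and housing heterogeneity tests compare odds ratios without saying so, and a markedly smaller percentage-point gain in severe or homeless patients could go undetected and unreported

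*SAP*

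**What the plan says.** - **Model.** SAP, Primary Hypothesis 1: "A mixed effects logistic regression model [2,3] will be used to compare the binary outcome of hair and urinalysis-confirmed abstinence".
- **Test.** SAP, Heterogeneity of treatment effects: "the mixed effects models and survival analyses used to test the primary hypotheses will be modified". For psychiatric severity, the change consists of adding a two-level indicator and its product with condition. OUD severity and housing are handled in the same way.
- **Reading of the test.** "A significant interaction would indicate that the effects of the intervention vary as a function of a patient's psychiatric severity". No effect scale is attached to this statement.
- **What follows.** "If the interaction term is significant, the treatment effect will be estimated separately at each level". Nothing is planned by level if the term is not significant.
- **Motive.** Of the three variables: "Each of these variables should negatively impact treatment outcomes, and could suppress differences between conditions". Again no scale is named.
- **Effect sizes.** SAP, Power for the Primary Hypotheses, speaks of "80% power to detect an approximately 15% difference in abstinence rates between the conditions" and gives an odds ratio beside every percentage-point difference.

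**The concern.** In a logistic model the null hypothesis of the product term is that the odds ratio is the same at both levels. Whether that also means the same gain in abstinent patients depends on the SC rates. If those are similar across levels, the two questions nearly coincide. If they differ and PATH works, they generally do not. The SAP expects the three variables to lower outcomes, so the second case is the one it anticipates.

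Two misreadings become possible. A non-significant term may be taken as homogeneous benefit although severe or homeless patients gain far fewer percentage points. Because estimates by level depend on significance, that shortfall may never be shown. Conversely, a significant term may be taken as unequal benefit although the percentage-point gains are the same. An FQHC planning services for severe or homeless patients would want the absolute gain in each group.

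**Working it through.** **Inputs from the documents.** 800 patients, 400 per condition (protocol, section 4). SC abstinence 25%, within-patient correlation .50 with compound symmetry, 20% attrition at the last visit, alpha .025 per primary hypothesis (SAP, Power for the Primary Hypotheses; also protocol, section 5). Six follow-up visits (SAP, Primary Hypothesis 1). Sidedness is not stated, and two-sided is assumed. No alpha is given for the interaction tests, so .05 is used, with .025 in brackets.

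**Assumptions.** Half the patients at each level; SC rates (severe/other) of 10%/40%, 15%/35% or 20%/30%, each averaging the plan's 25%.

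**Step 1: the plan's own figure.** Averaging six visits multiplies the variance by (1 + 5 × .50)/6 = 0.583. With 133 × 0.8 = 106.4 patients per condition, the effective number is 106.4/0.583 = 182.4. For 25% vs 40%:

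power = Φ[(0.15√182.4 − 2.241√(2 × .325 × .675)) / √(.25 × .75 + .40 × .60)] = Φ[(2.026 − 1.485)/0.654] = Φ(0.83) = 79.6%.

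The SAP states 80%. The odds ratio is (.40/.60)/(.25/.75) = 2.00, as stated. The method therefore matches the plan's.

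**Step 2: what a common odds ratio implies.** From SC rate p, an odds ratio OR gives a gain d = p(1 − p)(OR − 1)/[1 + p(OR − 1)]. This rises with p up to p = 1/(1 + √OR), which is 0.41 for OR 2.0. All the SC rates used here lie below that point, so different rates give different gains. With OR 2.0:

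- 10%/40%: .09/1.10 = 8.2 vs .24/1.40 = 17.1 points (48%)
- 15%/35%: 11.1 vs 16.9 points (66%)
- 20%/30%: 13.3 vs 16.2 points (83%)

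In all three cases the product term is significant only at its nominal error rate.

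**Step 3: rejection rates.** Each of the four level-by-condition cells has 200 patients, so 200 × 0.8/0.583 = 274.3 effective. The standard errors are √[Σ 1/(p(1 − p))/274.3] for the log ratio of odds ratios and √[Σ p(1 − p)/274.3] for the difference between rate differences.

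*Halved gain at 10%/40%* (10→17.5%, 40→55%). Odds ratios 1.91 and 1.83; log ratio 0.040; SE = √(26.24/274.3) = 0.309; z = 0.13; power 5%. On the rate scale the contrast is 0.075; SE = √(0.7219/274.3) = 0.0513; z = 1.46; power 31%.

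*Equal gain of 15 points at 10%/40%* (10→25%, 40→55%). Odds ratios 3.00 and 1.83; log ratio 0.4925; SE = √(24.65/274.3) = 0.300; z = 1.64; significant in 38%.

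| SC severe/other | Equal 15-point gains: odds ratios | Product term significant | 7.5 vs 15 points: odds ratios | Product term | Rate contrast |
|---|---|---|---|---|---|
| 10%/40% | 3.00, 1.83 | 38% (28%) | 1.91, 1.83 | 5% (3%) | 31% (22%) |
| 15%/35% | 2.43, 1.86 | 16% (10%) | 1.65, 1.86 | 7% (4%) | 29% (20%) |
| 20%/30% | 2.15, 1.91 | 7% (4%) | 1.52, 1.91 | 14% (8%) | 28% (19%) |

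**Step 4: checks.** Step 3 uses marginal odds ratios, whereas the planned model has conditional ones. With a random-intercept SD of 2.89, chosen to give correlation .50 at 25%, equal 15-point gains at 10%/40% correspond to conditional odds ratios of 7.9 and 3.6. A common conditional odds ratio of 4.16 (that for 25→40%) gives gains of 9.4 vs 16.7 points (56%). The direction is unchanged, and the imbalance in gains is somewhat smaller.

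A simulation fitting a random-intercept logistic model gave 37%, 15% and 7–8% for the equal-gain scenarios at .05. It contained condition, severity and their product, but not the planned time terms or baseline abstinence.

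Spreading the attrition evenly over the visits and keeping the visits made before dropout changes the combined variance factor from 0.583/0.8 = 0.729 to 0.622, so 200/0.622 ≈ 322 effective per cell. At 10%/40% the equal-gain figure becomes 43% (z = 0.4925/√(24.65/322) = 1.78). For the halved gain the product term stays at 5% and the rate contrast rises to 35%.

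**The case against.** Several stronger readings are tempting, and the documents do not support them.

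- **That the plan asks about percentage points and tests something else.** The heterogeneity section speaks of suppressed differences without naming a scale or singling out abstinence, and the power section pairs every difference with an odds ratio. The rate reading is reasonable, but it is an inference. What the documents do show is that the scale is unstated.
- **That the interaction test has inflated type I error.** When gains are equal and SC rates differ, the odds ratios really do differ, so rejecting is correct for that test's null. The fault is in an unqualified interpretation.
- **That every heterogeneity test is affected.** The retention tests use a Cox model and concern hazard ratios, a separate matter. For setting and opioid type (SAP, Primary Hypothesis 1: "We will use similar mixed effects logistic regression models (described above) that will additionally include terms for the specific subgroup variable and its interaction" with condition), the plan does not expect different SC rates; its power calculations use the same specifications in each subgroup.
- **That a halved benefit will typically be missed because of the scale.** A common odds ratio of 2.0 roughly halves the gain only with a gap as wide as 10% vs 40%.
- **That the rate scale should replace the odds-ratio scale.** The rate contrast has the mirror-image property: at 10%/40% with identical odds ratios of 2.0 it would be significant in just over 40% of trials. Its power for a halved gain is also modest, near 30%. Preferring one scale outright is a matter of judgement.

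The SAP also follows cited guidance on heterogeneity that cannot be consulted here, so what that guidance says on scale is unknown. Nor does the SAP forbid reporting effects by level after a non-significant test; it simply makes no provision for it.

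**Conclusion.** The point holds as a minor one, for abstinence and for psychiatric severity, OUD severity and housing. The plan draws a scale-free conclusion from an odds-ratio test and makes estimates by level conditional on that test, in the setting where it expects outcomes to differ by level.

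Under an assumed SC gap of 10%/40%, the product term has essentially no power above alpha to show a gain of 7.5 against 15 points, and is significant in close to 40% of trials when the gains are equal. At 20%/30% the second problem nearly vanishes (7–8%), and power for the halved gain is still only about 14%. All these figures rest on SC rates by level and an even split that the documents do not give. The primary comparison of PATH with SC is not affected.

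**What to change.** In the SAP section on heterogeneity of treatment effects:

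1. State that for abstinence the product term tests heterogeneity on the (conditional) odds-ratio scale.
2. For each of the three variables, report model-based marginal abstinence rates by condition, the PATH minus SC difference at each level, and the difference between those differences, all with confidence intervals (delta method or patient-level bootstrap), whatever the interaction p-value.
3. Where the two scales disagree, describe the conclusion as specific to the scale.

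The same reporting may be extended to setting and opioid type, where the case for it is weaker.

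The cost is a few sentences and a post-estimation step on models already planned. The downside is a second heterogeneity result per variable. It adds multiplicity and has modest power, so it should be read mainly through its confidence interval.

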
Secondary Hypotheses: Relative to those in the SC condition, participants in the PATH condition will demonstrate:

- **Lower rates of service utilization (days of hospitalizations, emergency department visits, residential treatment)**
- **Higher quality of life (Q-LES-Q-SF scores)**
- **Lower rates of HIV risk behaviors (RAB total, sex, and drug risk scores)**

Exploratory Hypotheses: Relative to those in the SC condition, participants in the PATH condition will demonstrate:

- **Improved Employment, Family/Social Functioning, and Psychiatric severity scores on the ASAM Criteria.**

Mixed effects models [2] will be used to compare the treatment conditions on each secondary and exploratory outcome at months 6, 12 and 18. Each model will include terms for treatment condition, time, and their interaction, and the baseline value of outcome measure along with any other necessary covariates. Subgroup analyses similar to those outlined above will be conducted to establish the heterogeneity of the treatment effects. Count data (i.e., service utilization variables) will be analyzed using PROC GLIMMIX specifying a poisson distribution and continuous data (i.e., quality of life, HIV risk scores, and psychosocial severity scores) will be analyzed using PROC MIXED.

Missing values. Missing data will not be an issue for some of the outcomes (i.e., time in treatment). The most important source of missing data in this study is likely to be from participant dropout. We will analyze the data under an intent-to-treat principle in which all participants initially randomized will be included [17]. In addition, mixed effects models will provide valid estimates of intervention efficacy if the missing data are ignorable. We will evaluate the patterns of missing data for each outcome and conduct logistic regression and survival analysis models predicting dropout using client characteristics and accrued measures to determine whether the dropout process is ignorable (i.e. whether missed visits are well explained by observable data). We will examine the impact of missing data by comparing results from models in which missing data are imputed and through pattern-mixture models [18] that examine how responses vary as a function of the pattern of missing data.

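### Subgroup effects of PATH are estimated only after a significant interaction, which exaggerates those reported and leaves the rest out; a significant interaction is read as heterogeneity with no account taken of at least 12 tests

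*SAP*

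**What the plan says.** - **Modifiers.** SAP, Primary Hypothesis 1, names setting and opioid type as primary subgroups and medication type as an exploratory one. Primary Hypothesis 2 repeats all three for retention. The section on heterogeneity of treatment effects adds psychiatric severity, OUD severity and housing, on both primary outcomes.
- **Gate.** Primary Hypothesis 1: "In the event that the interaction is significant, the treatment effect will be estimated separately at each level of the categorical variable". Primary Hypothesis 2 and the heterogeneity section carry the same condition.
- **Interpretation.** The heterogeneity section: "A significant interaction would indicate that the effects of the intervention vary as a function of" the patient's psychiatric severity, glossed there as meaning that treatment effects are heterogeneous. OUD severity and housing are to be handled in the same way.
- **Alpha.** Power for the Primary Hypotheses: "The analysis was based on a corrected alpha of .025 (.05/2 primary outcomes), a compound symmetry covariance structure". Then: "We have chosen to use an alpha level that corrects for the number of primary hypotheses rather than the number of subgroup analyses", because "the latter approach would substantially increase the likelihood of making a type 2 error". Protocol item 5 says the same. Neither document says which level applies to the interaction tests.
- **Other outcomes.** Under the secondary and exploratory hypotheses: "Subgroup analyses similar to those outlined above will be conducted to establish the heterogeneity of the treatment effects". No number of tests is given.

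**The concern.** Two features work together. First, many interactions are tested and a significant one is taken to show heterogeneity, with nothing in the reading rule that reflects how many were tried. Second, subgroup effects are produced only for interactions that pass the test. An estimate that is seen only when it is extreme is biased away from the truth. The subgroups that do not pass have no promised estimate at all, although the SAP computes 80% power for the PATH versus SC effect within each of the four primary subgroups. At stake are the size and credibility of any statement that PATH's effect differs between kinds of patient, and the availability of the subgroup results the trial was sized to give.

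**Working it through.** **1. The plan's own figures.** Abstinence, time-averaged difference over 6 visits, correlation .50, two-sided .025, 80% power, 20% loss applied at every visit:

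n per arm = (z.9875 + z.80)² × [p1q1 + p2q2] × [(1 + 5 × .5)/6] / d² / (1 − .20)

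- 25% vs 40%: 131.7, against 133 stated.
- 12 points for IP or OP: 202.4, against 200 stated.
- Overall, OR 1.5: 408.9, against 400 stated.
- Heroin does not reproduce this way: OR 1.6 needs 300 per arm against 267. With 10% average loss it needs 266.7.

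Retention at .025 gives power of 79.6%, 81.0%, 81.4% and 81.7% for HR .59, .65, .69 and .74. The figures therefore fit a two-sided .025 used for the effect *within* each subgroup. No power is given for any interaction.

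**2. Number of tests.** 6 modifiers × 2 primary outcomes = 12.

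**3. Chance of at least one false hit if PATH's effect is uniform.** Modifiers are assumed independent.

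- Outcomes uncorrelated: 1 − .975¹² = 26.2%; 1 − .95¹² = 46.0%.
- Outcomes correlated .8: the chance that at least one of a modifier's two tests is significant is .0402 at .025 and .0781 at .05. So 1 − (1 − .0402)⁶ = 21.8%, and 1 − (1 − .0781)⁶ = 38.6%.
- The two primary subgroups alone (4 tests): 8-10% at .025, 15-19% at .05.

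**4. What the gate does to the estimates.** Setting, 200 per arm in each group, 25% vs 33% (8 points) in both, risk-difference scale:

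- SE within a setting = √{[.25 × .75 + .33 × .67] × (3.5/6) / (200 × .8)} = .0386.
- SE of the interaction = .0386 × √2 = .0546.
- Under no interaction, the mean of |z| given |z| > c is 2φ(c)/α. This is 2.338 at .05 and 2.589 at .025.
- Mean reported gap: 2.338 × .0546 = 12.8 points; 2.589 × .0546 = 14.1 points.
- The average of the two groups stays at 8, so the estimates are 8 ± 6.4 (about 14 vs 2) at .05 and 8 ± 7.1 (about 15 vs 1) at .025.
- With 10% average loss: 14.0 vs 2.0, and 14.7 vs 1.3.

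A real 8-point interaction is detected 31% of the time at .05 (22% at .025), and the reported gap then averages about 14 (15) points.

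**5. The same on the log-odds scale, which the model uses.** The stated OR of 1.8 per setting implies an SE of ln 1.8 / 3.083 = .191, so .270 for the log ratio of ORs. 80% power at .025 needs a ratio of about 2.3. For a true ratio of 1.5, power is 23% at .025 or 32% at .05, and a significant log ratio is inflated 1.9-fold or 1.7-fold on average. No ratio below 1.83 (.025) or 1.70 (.05) can reach significance.

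**6. What goes unreported.** For any one modifier and outcome with a uniform effect, the interaction is non-significant with probability 1 − α: 97.5% at .025, 95% at .05. The rule then calls for no separate subgroup estimate.

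**The case against.** The plan does several things well. The modifiers are prespecified, every subgroup claim needs an interaction test, and medication type is labelled exploratory. The choice not to correct for subgroups is open and reasoned. All of that stands, and it makes a formal correction a matter of judgement. It does not answer the gate: prespecification does not remove selection bias, and the type 2 error argument concerns the level of each test, not whether estimates are shown.

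A reader might infer more than the documents support:

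- *That the tests have no alpha control at all.* The SAP ties its subgroup work to a level already halved to .025. Whether that level governs interactions is unstated, so both are shown here.
- *That a false heterogeneity claim is more likely than not.* On the 12 primary-outcome tests it is below one half at either level.
- *That there are 30 further tests, 42 in all.* The SAP gives no number. Three modifiers on 7 secondary and 3 exploratory outcomes would give 30, but 20 (two modifiers) or 60 (six) are also possible. Of the 42, 18 would already be labelled exploratory: 12 for medication type, and 3 outcomes × 2 other modifiers = 6.
- *That PATH would be declared to work in one group and not another.* The SAP says only that effects vary.

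It can also be said that the interaction model is fitted regardless and its coefficients contain the subgroup effects. That is true, but the SAP does not commit to reporting them unless the test is significant.

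**Conclusion.** The point holds as a reporting and interpretation fault, not as a breach of type 1 error control on the primary hypotheses. The selection effect is the firmer part, since it arises for any single modifier and needs no count of tests. In the setting example it turns a uniform 8 points into about 14 vs 2 or 15 vs 1. That example rests on the SAP's own power inputs, a flat 20% loss (the SAP gives 20% at the final visit only) and the risk-difference scale; lower loss or the log-odds scale does not change the conclusion. The 22-26% and 39-46% figures assume independent modifiers, two-sided tests and a correlation of 0 to .8 between the two outcomes. The subgroup analyses of secondary and exploratory outcomes add to the count by an amount the documents do not fix.

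**What to change.** - **SAP, Primary Hypotheses 1 and 2, and heterogeneity of treatment effects.** Replace the conditional rule with: *PATH vs SC effects with confidence intervals are estimated and reported at every level of each subgroup, together with the interaction estimate and its interval, whether or not the interaction is significant.* Apply the same rule to the subgroup analyses of secondary and exploratory outcomes.
- **SAP, heterogeneity of treatment effects.** Replace the statement that a significant interaction indicates heterogeneity with: *A significant interaction is evidence of heterogeneity, to be read alongside the number of interaction tests performed.*
- **SAP, secondary and exploratory hypotheses.** Change the stated purpose of the subgroup analyses from establishing heterogeneity to exploring it.

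Cost: SAP wording and some extra table rows; no new data, no loss of power and no change to the primary tests.

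A Holm correction over the four primary interaction tests is optional and not part of this fix. It has a real price: at its first step (.0125), power for a 12-point setting interaction falls to 38%, from 59% at .05 or 48% at .025.
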